#### **8.2.2** Exclusion Criteria

A subject will be excluded from the study if the subject meets any of the following criteria:

- 1. Joint replacement surgery of the index knee at any time, or open surgery of the index knee in the past 24 months. Joint replacement of the contralateral knee is permitted for subjects who will not receive an injection in the contralateral (natural) knee. For subjects with bilateral knee OA who will receive an injection into both knees, joint replacement surgery of both knees at any time, or open surgery of the index knee in the past 24 months, is excluded.
- 2. Prior arthroscopic surgery of the index knee within 6 months of Screening.
- 3. Any painful conditions of the index knee due to joint disease other than OA. For example, radicular or referred pain involving the index knee or from joint disease other than OA involving the index knee, such as, but not restricted to chondromalacia patellae, inflammatory diseases (e.g., rheumatoid arthritis, psoriatic arthritis), metabolic diseases, gout/pseudogout, hemochromatosis, acromegaly, etc.
- 4. Periarticular pain from any cause, including referred pain, bursitis, tendonitis, soft tissue tenderness, or subacute/acute pain from injury.
- 5. Other chronic pain anywhere in the body that requires the use of chronic analgesic medications, including, but not limited to, local painful areas, myofascial pain syndromes, fibromyalgia, genetic, metabolic abnormalities, hematologic, or neuropathic pain.
- 6. Instability of the index or contralateral knee (e.g., cruciate ligament tear or rupture, significant protruding meniscus, substantial ligamentous laxity, unstable PJR or TJR).
- 7. Misalignment (>10 degrees varus or valgus) of the index knee on standing.
- 8. Documented history of neuropathic arthropathy or finding of bony fragmentation in the index knee with imaging (radiographic, computed tomography, or magnetic resonance imaging).
- 9. Physical/occupational/chiropractic therapy for the lower extremities or acupuncture for the lower extremities within 15 days of Screening, or need for such therapy during the study.
- 10. Plans to have surgery, other invasive procedures, or IA injections (other than CNTX-4975-05) for either knee while participating in the study.
- 11. Current use of opioids for any condition other than for OA of the knees injected with CNTX-4975-05) (maximum dose of 15 mg of hydrocodone [or equivalent] per day).
- 12. Corticosteroid injection into the index or contralateral knee within 90 days of Screening.
- 13. Received IA viscosupplementation (e.g., Synvisc®, Hyalgan®) within 90 days of Screening.
- 14. History of allergic reaction to the planned local anesthesia/analgesic regimens, ethylenediaminetetraacetic acid, Kolliphor HS 15, butylated hydroxytoluene, or capsaicin.
- 15. Presence of any medical condition or unstable health status that, in the judgment of the investigator, might adversely impact the safety of the subject, or the conduct of the study, or negatively affect the resulting data, including chronic conditions that are likely to alter the rate of healing or are likely to result in safety complications unrelated to the study

medication, or significantly compromise key organ systems. For any question regarding eligibility, it is strongly recommended that the investigator discuss the subject with the medical monitor.

- 16. Is pregnant or is breast feeding.
- 17. Has a malignancy, a history of malignancy, or has received treatment for malignancy at any time, with exception of resected and cured basal cell carcinoma and squamous cell carcinoma of the skin.
- 18. Regular use of anticoagulant blood thinners (except low-dose aspirin, Dabigatran 150 mg once daily [qd], Enoxaparin 40 mg qd, Rivaroxaban 10 mg qd, or Apixaban 2.5 mg twice daily [bid], or clopidogrel 75 mg qd, which are allowed).
- 19. Active cutaneous disease at the anticipated site of CNTX-4975-05 injection that would prevent the safe administration of CNTX-4975-05.
- 20. Ulcer or open wound anywhere on the index knee.
- 21. Specific laboratory abnormalities:
  - Hemoglobin <11.0 g/dL

  - White blood cells  $< 2.5 \times 10^9/L$
  - Neutrophils  $< 1.5 \times 10^9/L$
  - Platelets  $<100 \times 10^9/L$
  - Aspartate transaminase or alanine transaminase >2 × upper limit of normal
  - Creatinine >1.6 mg/dL
  - Glucose (fasting) >250 mg/dL
  - Hemoglobin A1c (HgbA1c) >9.0%
- 22. Clinically significant abnormal laboratory result at the Screening Visit (in the opinion of the investigator), or significant organ disease that would put the subject at undue risk or affect the ability of the subject to participate in the trial. For any question regarding eligibility, it is strongly recommended that the investigator discusses the subject with the medical monitor.
- 23. Use of an investigational medication within 30 days of Screening or 5 pharmacokinetic or pharmacodynamic half-lives (whichever is longer), or scheduled to receive such an agent while participating in the current study.
- 24. Prior participation in an ALGRX 4975 or CNTX-4975 study.
- 25. Has any of the following characteristics:
  - Active or historic substance use disorder within the previous year, as defined by the Diagnostic and Statistical Manual for Mental Health Disorders, fifth edition
  - Test is positive upon urine drug screen for a substance of abuse (prescribed opioids acceptable)
  - Has a history, at any time, or currently, of suicidal ideation, suicide attempt, or increased risk of suicide

- Has an unacceptable level of depression or anxiety as measured by the Hospital Anxiety and Depression Scale (HADS) (a score of ≥11)
- Has unacceptable chronic pain as measured by the Fibromyalgia Symptom Scale Score (FSS) (a score of ≥13)
- Has a positive pregnancy test at the Screening or either Treatment Visit
- Has ongoing litigation for workers' compensation
- Has any condition, or is taking any medication, that would be contraindicated for study participation

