### 8.2 Study Entry Criteria

#### 8.2.1 Inclusion Criteria

A subject will be eligible for study participation if the subject meets all of the following criteria:

- 1. Male or female subjects between 40 and 95 years of age (inclusive).
- 2. Confirmation of OA of the knee: radiography of both knees using standard standing films (scored by the investigator) or using the fixed flexion method, taken during the Screening Visit (prior radiographs of the knees of sufficient quality that have been taken within 2 years of the Screening Visit may be used for K-L grading). The index knee must show evidence of chronic OA with a K-L grade of 1, 2, 3 or 4. Subjects who were screen failures for the US CNTX-4975i-OA-301 or CNTX-4975i-OA-304 trials may be considered for this trial if the K-L grade of the index knee is 1-4, inclusive.
- 3. Confirmation of OA of the index knee: American College of Rheumatology (ACR) diagnostic criteria (ACR confirmation of bilateral knee OA for subjects who will have bilateral knee injections of CNTX-4975-05).
- 4. For subjects for monoarticular knee injection, the index knee must have moderate to severe pain (≥5 and ≤9) at screening associated with OA, which must be stable for a minimum of 6 months prior to Screening, as assessed by the investigator. These subjects may have:
  - a) unilateral or bilateral OA, with the index knee having moderate to severe pain, and the contralateral knee having none to mild pain, OR
  - b) unilateral or bilateral OA, with the index knee having moderate to severe pain and the other knee having had a PJR or TJR within 5 years of the Screening Visit. The knee with the PJR/TJR is not to be injected with CNTX-4975-05.

For subjects for bilateral knee injection, the index knee must have moderate to severe pain  $(\ge 5 \text{ and } \le 9)$  at screening associated with OA, and greater pain in the index knee than in the contralateral knee. Their pain must be stable for a minimum of 6 months prior to Screening, as assessed by the investigator. The index knee in these subjects is the one with the worst pain with walking. Where both knees have equal pain with walking, then the knee on the subject's dominant side will be designated the index knee.

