### 9.12.2 Prohibited Therapies

The following therapies are prohibited both prior to and during the study:

- Injection of corticosteroids in the index knee from 90 days prior to Screening through study completion.
- Current use of opioids for any condition other than for OA of the injected knees or PJR/TJR knees (maximum dose of 15 mg of hydrocodone [or equivalent] per day as background medication allowed at entry).
- Regular use of anticoagulant blood thinners (except low-dose aspirin, Dabigatran 150 mg qd, Enoxaparin 40 mg qd, Rivaroxaban 10 mg qd, or Apixaban 2.5 mg bid, which are allowed).
- Use of an investigational medication within 30 days or 5 pharmacokinetic or pharmacodynamic half-lives (whichever is longer) prior to Screening or while participating in the study.
- Physical/occupational/chiropractic therapy for the lower extremities or acupuncture for the lower extremities within 15 days of Screening, or need for such therapy during the course of the study.
- Joint replacement surgery of the index knee at any time, or open surgery of the index knee in the past 24 months prior to Screening, or prior arthroscopic surgery of the index knee within 6 months of Screening. For subjects with bilateral knee OA who will receive an injection into both knees, joint replacement surgery of both knees at any time, or open surgery of the index knee in the past 24 months, is excluded.
- Surgery, or other invasive procedures, or IA injections (other than CNTX-4975-05) while participating in the study.
- Subjects should not take a hot bath or shower, or expose the injected knee(s) to external heat, within 12 hours after the injection.

13-Jun-2019

The subject should be excluded from study participation if they have taken any medication prior to treatment that would indicate that the subject has a serious or unstable illness, is not in good general health, or has a condition that would contraindicate study participation.

Subjects receiving excluded therapies will be ineligible for study enrollment. If subjects receive excluded therapies after enrollment, continuation in the study will be at the discretion of the sponsor/investigator/medical monitor.

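### Six exclusion provisions name only the index knee, so the second knee of a bilateral subject can be injected despite a condition that bars the first

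*Combined protocol and SAP*

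**What the plan says.** Section 9.5 assigns type 2 subjects an injection into each knee, one week apart. Section 8.2.1, inclusion 4, fixes which of the two is the index knee: "The index knee in these subjects is the one with the worst pain with walking". A tie goes to the dominant side. The other injected knee is called the contralateral knee.

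Section 8.2.2 then limits several exclusions to the index knee:

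- Exclusion 1, in the sentence written for subjects who will be injected in both knees, ends "or open surgery of the index knee in the past 24 months, is excluded".
- Exclusion 2 bars arthroscopy of the index knee in the 6 months before Screening. Section 9.12.2 repeats this: "or prior arthroscopic surgery of the index knee within 6 months of Screening".
- Exclusion 3 bars painful joint disease other than OA in the index knee.
- Exclusion 7: "Misalignment (>10 degrees varus or valgus) of the index knee on standing".
- Exclusion 8, imaging clause: "finding of bony fragmentation in the index knee with imaging".
- Exclusion 20: "Ulcer or open wound anywhere on the index knee".

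Other exclusions in the same list reach the second knee. Exclusion 12 reads "Corticosteroid injection into the index or contralateral knee within 90 days of Screening". Exclusion 6 (instability) also names both knees, and exclusion 10 (planned surgery, procedures or other injections) covers either knee.

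**The concern.** The sponsor judged each listed condition sufficient reason not to inject a knee. A type 2 subject's second knee receives the same product by the same route, and the documents give no reason to hold it to a lower standard. Whether a recently operated or wounded knee may be injected then depends only on whether it is the more painful of the two.

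The main stake is subject safety, most plainly for a knee with an open wound or recent open surgery. A secondary stake is the bilateral OMERACT-OARSI responder rate in Section 13.1.2, which requires both knees to respond. Painful non-OA disease in the second knee could make a subject a non-responder for a reason unrelated to OA.

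**Working it through.** There is no plan figure to reproduce. The check reads each exclusion for the knee it names, and then asks whether any other text closes the gap.

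**Step 1. Which knee each provision names (Section 8.2.2)**

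| Exclusion | Knee covered |
|---|---|
| 1, open surgery within 24 months | Index only, including in the sentence for bilateral subjects |
| 2, arthroscopy within 6 months | Index only |
| 3, painful non-OA joint disease | Index only |
| 7, misalignment over 10 degrees | Index only |
| 8, bony fragmentation on imaging | Index only |
| 20, ulcer or open wound | Index only |
| 6, 12 | Index and contralateral |
| 10 | Either knee |
| 19, skin disease | The intended injection site |
| 4, 13, neuropathic arthropathy clause of 8 | No knee named |

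Four exclusions are limited to the index knee in full (2, 3, 7, 20) and two in part (1, 8). The synopsis repeats this wording, and Section 9.12.2 repeats it for open surgery and arthroscopy.

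**Step 2. Is joint replacement part of the gap?** No. Exclusion 1 allows a replaced contralateral knee only when that knee will not be injected. Inclusion 4 bars injecting a replaced knee, and the synopsis entry on treatment regimens limits bilateral injection to subjects without joint replacement.

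**Step 3. Does other text cover the second knee?**

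- Inclusion 2 requires "radiography of both knees using standard standing films (scored by the investigator"), but a finding of fragmentation or misalignment in the second knee triggers no listed exclusion.
- Inclusion 3 requires ACR confirmation of OA in both knees. That does not rule out a coexisting disease, recent surgery or a wound.
- Exclusion 4 covers periarticular and referred pain and overlaps part of exclusion 3. It does not reach intra-articular non-OA disease such as gout.
- Exclusion 19 covers skin disease only at the injection site. Exclusion 20 covers a wound anywhere on the knee, but only the index knee.
- Exclusion 15 and the last item of exclusion 25 are general and set no 6-month, 24-month or 10-degree limit.
- Visit 4 (Section 10.1.4) has a partial examination and an erythema and edema check before the second injection. No rule says that a listed finding stops that injection.

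**Step 4. Timing.** The Schedule of Events and Section 10.1.1 place the eligibility check at Screening only. Visit 4 is Day 7 with a window of -2/+5 days:

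- earliest: 7 - 2 = Day 5
- latest: 7 + 5 = Day 12

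Screening may be up to 14 days before Day 1, and Day 1 to Day 12 is 11 days. The longest standard interval from Screening to Visit 4 is therefore about 14 + 11 = 25 days. It can be longer at sites using the 14-business-day scheduling allowance in the Schedule of Events footnote.

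**Step 5. Scope.** The type 2 target is at least 150 subjects (Section 7.1) and the planned total is about 850 (Section 13.2): 150 / 850 = 0.176, or 17.6%. This is the share of subjects with a second injected knee. It is not the share whose second knee has a listed condition.

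**The case against.** The strongest reply is that this is loose drafting. The protocol elsewhere writes index knee where every injected knee must be meant. Section 9.3.3 asks for needle position to be confirmed in the index knee. Section 10.3.3.3 describes procedure pain in the index knee, although Section 10.1.4 collects it when the other knee is treated. Section 9.12.2 limits the corticosteroid ban to the index knee, while exclusion 12 names both. This may well explain how the wording arose, but it does not settle how a site should read it. The same list separates one knee from both in exclusions 6, 10 and 12. Exclusion 1 is the clearest case, because its sentence for subjects injected in both knees still confines open surgery to the index knee.

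A second reply is that further cover exists:

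- Inclusion 4 requires bilateral subjects' pain to have been stable for 6 months, as judged by the investigator.
- Exclusions 5 (other chronic pain needing analgesics) and 9 (recent lower-limb therapy) are not tied to a knee.
- Section 8.3 lets the investigator withdraw a subject in that subject's interest.
- The investigator examines the subject before each injection and would be likely to see an open wound.

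This lowers the practical risk, and many investigators would decline such an injection. All of it is partial or a matter of judgment, however, and none of it sets the missing limits for the second knee.

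Third, the documents do not say why these exclusions exist. Misalignment, arthroscopy and non-OA disease could be excluded to keep pain attributable to OA rather than for safety. That is fair: the safety argument is strongest for wounds and recent open surgery. The bilateral responder objective is also descriptive (Section 6.2), so the effect on that endpoint is a possibility only.

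Fourth, a Visit 4 recheck gives the second knee something the index knee does not have at Visit 2. That is true. The reason for it is the longer interval since Screening, and it uses an examination already scheduled.

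**Conclusion.** The concern holds. Followed as written, the protocol permits injection of a type 2 subject's second knee with a condition that would bar the index knee, under four exclusions in full and two in part. At least 150 of about 850 subjects (17.6%) are exposed to the gap, assuming the type 2 target is met. The number of second knees actually affected cannot be estimated from the documents, and investigator judgment would prevent some of these injections. The primary endpoint uses the index knee and is untouched. Joint replacement is already covered. This should be corrected as an inexpensive gain in subject safety; it does not threaten the trial's main comparison. Confidence is medium, because the intended meaning may have been broader than the text.

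**What to change.** Replace *index knee* with *any knee to be injected* in exclusions 1 (open-surgery clause), 2, 3, 7, 8 (bony-fragmentation clause) and 20. Make the same change to the open-surgery and arthroscopy limits in Section 9.12.2 and to the matching synopsis text. State in Section 10.1.4 that the second knee is rechecked against exclusion 20 at the existing pre-injection examination, and that an ulcer or open wound stops the injection. As a copy-edit, change *both knees* to *either knee* in the joint-replacement clause for bilateral subjects.

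The cost is an amendment to the wording plus one explicit check within an examination already planned. Films of both knees are already required. Expect some additional screen failures among bilateral candidates; their number cannot be estimated from the documents. These candidates cannot move to type 1, which requires no more than mild pain in the other knee.

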### 8.3 Premature Subject Withdrawal

All subjects will be advised that they are free to withdraw from participation in this study at any time, for any reason, and without prejudice. Every reasonable attempt should be made by the investigator to keep subjects in the study. However, subjects must be withdrawn from the study if they withdraw consent to participate. Investigators must attempt to contact subjects who fail to attend scheduled visits by telephone or other means to exclude the possibility of an AE being the cause of withdrawal. Should this be the cause, the AE must be documented, reported, and followed as described in Section 11.2.

The sponsor reserves the right to request the withdrawal of a subject due to protocol deviations or other reasons.

The investigator also has the right to withdraw subjects from the study at any time for lack of therapeutic effect that is intolerable or otherwise unacceptable to the subject, for intolerable or unacceptable AEs, intercurrent illness, noncompliance with study procedures, administrative reasons, or in the investigator's opinion, to protect the subject's best interest.

If a subject is withdrawn before completing the study, the reason for withdrawal and the date of discontinuation will be recorded on the appropriate page of the electronic case report form (eCRF). Whenever possible and reasonable, the evaluations that were to be conducted at the completion of the study should be performed at the time of premature discontinuation.

### 8.4 Subject Replacement Criteria

Withdrawn subjects will not be replaced. If a substantial number of subjects are withdrawn from the study, the sponsor will evaluate the need for developing replacement criteria.

Enrolled subjects withdrawn from the study may not reenter. The subject number for a withdrawn subject will not be reassigned to another subject.

#### 9 TREATMENTS

### **Identification of Investigational Product(s)**

Investigational product will be provided Labeling and Packaging

Labeling and packaging of CNTX-4975-05 will be performed

#### 9.3 **Treatments Administered**

All subjects will receive CNTX-4975-05 injected IA into the index knee; subjects with bilateral OA will receive an IA injection into both knees (injections will be separated by 1 week).

#### 9.3.1 Pre-Medication

Prior to the injection procedure, the investigator may, at his or her discretion, pre-medicate subjects with an oral dose of an opioid or NSAID. The skin at the point of the anticipated injection(s) may also be infiltrated with 1 to 2 mL of lidocaine and/or a topical analgesic such as ethyl chloride spray. It is recommended not to use more than 2 methods of local analgesia about the knee(s) to be injected.

### 9.3.2 Joint Treatment Regimens

All subjects are required to be administered an IA injection of a full 15 mL of lidocaine [without epinephrine] (1% or 2%, depending on the assigned treatment regimen) to ensure: 1) the local targeted concentration of CNTX-4975 in the joint; 2) distension of the joint capsule to improve access of CNTX-4975 to the joint space; and 3) to provide some analgesia. The full 15 mL of lidocaine (without epinephrine) and the full CNTX-4975-05 must be injected into the knee joint, as directed. The 5 flexion-extension moves of the knee after IA CNTX-4975-05 is injected into the knee also improve access of CNTX-4975 to the entire joint space. The lidocaine may have some modest effect on pain, but the concentration and dispersion of CNTX-4975 into the joint are the primary reasons for lidocaine use.

All subjects must be monitored for at least 30 minutes (or longer, as required by the protocol) after study drug injection to ensure that they do not have a hypersensitivity reaction/anaphylaxis.

Each site will be randomly assigned 1 of the following 5 treatment regimens to be employed for ALL subjects at that site:

Group	Cooling Device	

 Pre-cool

 Lidocaine %

 Post-lido cool

	Needle	Post- dose cooling
1. Breg Cooling Control Group	Breg ice water pump	

15 mins

2% lidocaine

30 mins

	Separate needles for lidocaine and CNTX-4975-05	30 to 90 mins as needed
2. Gel Pack Cooling Group	Elasto- Gel	

40 mins

2% lidocaine

10 mins

	Separate needles for lidocaine and CNTX-4975-05	10 to 90 mins as needed
3. Shortened Gel Pack Cooling Group	Elasto- Gel	

30 mins

2% lidocaine

5 mins

	Separate needles for lidocaine and CNTX-4975-05	up to 90 mins as needed
4. Single Needle Injection Gel Pak Cooling Group-2% Lidocaine	Elasto- Gel	

45 mins

2% lidocaine

no cooling

	Single needle for lidocaine and CNTX-4975-05	up to 90 mins as needed
5. Single Needle Injection Gel Pack Cooling Group-1% Lidocaine	Elasto- Gel	

45 mins

1% lidocaine

no cooling

	Single needle for lidocaine and CNTX-4975-05	up to 90 mins as needed

See study manual for specific instructions on the use of the Breg Cooling Wrap and the Elasto-Gel Cooling Wrap.

- 1. **Breg Cooling Control Group** (used in protocols CNTX-4975i-OA-301 and CNTX-4975i-OA-304 for comfort and blinding of the protocols)
  - a. Controlled joint cooling wrap with an ice water pump system (Breg Cooler) will be applied 15 minutes prior to IA injection of the full 15 mL 2% lidocaine (without epinephrine) into the knee joint using standard aseptic techniques.
  - b. Inject IA the full 15 mL of 2% lidocaine (without epinephrine) into the knee joint using appropriate aseptic techniques.
  - c. Controlled cooling will be resumed for a further 30 minutes after the IA injection of the full 15 mL 2% lidocaine (without epinephrine) into the knee joint.
  - d. The cooling device will be removed, and CNTX-4975-05 IA injection will be administered using standard aseptic techniques.
  - e. Controlled cooling will be reapplied for a minimum of 30 minutes, and up to 90 minutes, as needed, after CNTX-4975-05 injection, depending on the subject's comfort. The cooling may be discontinued after a minimum of 30 minutes after IA CNTX-4975-05 injection, if the subject has a pain level that is acceptable for the subject and investigator (0-4 scale: none, mild, moderate, moderately severe, and severe).

